3. ENDPOINTS

3.1. Primary Endpoint

The safety endpoints are the incidence of treatment-emergent events (TEAEs), physical examination findings, and changes in vital signs, pulmonary function and electrocardiogram (ECG) measurements.

Pharmacokinetic (PK) endpoints are the summary of the pharmacokinetic parameters (e.g. C_{max}, AUC_{last}, and AUC_{inf}) for PK10571 across treatments, dose-linearity assessment and steady state assessment (after multiple dosing)

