5. RANDOMIZATION

Subjects will be randomized into one dose cohort and receive either PK10571 or placebo. Within each cohort, 6 subjects will receive active drug and 2 subjects will receive placebo.

For both the SAD and MAD parts each cohort, randomization will occur in 2 blocks as follows: In the first block, 2 subjects (sentinel subjects) will be randomized 1:1 to receive PK10571 or placebo; in the second block, 6 subjects will be randomized 5 PK10571: 1 placebo. If PK10571 is well-tolerated in the sentinel subjects, the remainder of the cohort (n = 6) will be randomized. There will be a minimum of 48 hours between dosing of the 2 sentinel subjects and the remainder of the cohort.

Gender distribution will be based on sequential screening of volunteers who meet entry criteria, with a minimum of 4 females per cohort, in order to ensure 2 females per active dose group. Subjects will be assigned numbers in an ascending order, based on successful completion of the screening process. Each subject will participate in only one cohort.

Subjects who withdraw from the study may be replaced at the discretion of the Principal Investigator and Sponsor.

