6.2.10. Concentration-Time Data

PART A:

Blood samples for pharmacokinetic analysis of PK10571 will be collected at 0 hour (predose), and then at 3, 10, 20, 30, 40 minutes, and 1, 2, 4, 8, 12, 24, 36, and 48 hours after study treatment administration as specified by the protocol amendment. For two blood samples were collected at 1 and 5 minutes, instead of one blood sample at 3 minutes, prior to the protocol amendment. For and above, the 3-minute sample was collected after the protocol amendment.

PART B:

If QD dosing: Blood samples for pharmacokinetic evaluation will be obtained prior to the first dose administration (predose) on Day 1 and Day 7, and at the following times: Day 1 and Day 7 at 3, 10, 20, 30, and 40 minutes and 1, 2, 4, 8, 12, 24, and 36 hours after dosing; predose on Days 3-6, and on Day 8, Day 9, Day 10, Day 14, and Day 35 (total 34 samples).

If BID dosing: Blood samples for pharmacokinetic evaluation will be obtained prior to the first dose administration (predose) on Day 1 and Day 7, and at the following times after each dose (2 per day) on Day 1 and Day 7: 3 and 30 minutes and 2, 8, and 12 hours. Blood samples will also be collected before the first dose on Days 3-6, and on Day 8, Day 9, Day 10, Day 14, and Day 35 (total of 30 samples).

If TID dosing: Blood samples for pharmacokinetic evaluation will be obtained prior to the first dose administration (predose) on Day 1 and Day 7, and at the following times after each dose (3 per day) on Day 1 and Day 7: 3 and 40 minutes and 6 hours. An additional sample will be obtained on Day 2 (12 hours after the 3rd dose on Day 1). Blood samples will also be collected before the first dose on Days 2-6, and on Day 8 (6 hours and 12 hours after the 3rd dose on Day 7), Day 9, Day 10, Day 14, and Day 35 (total of 30 samples).

For multi-capsule administrations (if required to achieve the dose), the first postdose blood collection will be performed 5 minutes after the start of study treatment administration.

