For summarization of the concentration-time data, concentrations below the limit of quantitation (BLQ) will be set to zero. Mean concentration-time profiles will be created for SAD (all cohorts), SAD male vs. female (all cohorts), MAD (all cohorts), MAD male vs. female (all cohorts), and MAD (Day 1 vs. Day 7) for each cohort. Mean concentration-time profiles will be created using nominal time. All subject concentration-time plots (all subjects in one plot for each cohort, SAD and MAD) will be created using actual time. Individual subject plots (one subject per plot) will be created for MAD (Day 1 vs. Day 7) using actual time.

For time points occurring before 1.00 hour, nominal time will be presented to 3 significant figures (i.e.: 0.0167, 0.050, 0.083, 0.167, 0.333, 0.500, and 0.667 hours postdose). After 0.667 h, time will be presented as 2 decimal places (i.e.: 1.00, 2.00, 4.00, 8.00, 12.00, 24.00, 36.00, and 48.00 hours postdose).

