6.11. Pharmacokinetic and Statistical Analyses

Pharmacokinetic analyses are outlined below. Other exploratory analyses may be conducted as well.

Statistical Comparison: Single Dose (Day 1, Reference) and Multiple Dosing (Day 7, Test): Part B

Comparison of the log-transformed pharmacokinetic parameters C_{max} and AUC_{0-24} for PK10571 across study days (Day 7 vs. Day 1) will be performed using an ANOVA model and the two one-sided t-tests procedure. The ANOVA model will include factors for subject, day, and cohort. The ratios of the geometric means and 95% confidence intervals will be reported. Statistical analyses will be performed using appropriate software, e.g., PhoenixTM WinNonlin® (Version 6.3 or higher, Certara L.P.) and/or SAS® (Version 9.3 or higher, SAS Institute Inc.).

SAS code will be of the form:

Assessment of Dose-proportionality: Power Model

The relationship between dose and exposure parameters will be examined graphically for Part A (C_{max}, AUC_{last}, AUC₀₋₂₄, and AUC_{inf}) and Part B (C_{max} and AUC₀₋₂₄, Days 1 and Day 7).

Evaluation of dose proportionality will be explored using power analysis.

To assess dose proportionality, the pharmacokinetic parameters after drug administration will be compared across each dose level.

Statistical analyses will be done using a power model with mixed effects (Smith, 2000)³ of the following general form:

$$ln(PK) = ln(\beta_0) + \beta_1 \cdot ln(Dose) + \varepsilon$$
,

where

PK is the pharmacokinetic parameter tested (e.g., C_{max} or AUC),

 $ln(\beta_0)$ is the y-intercept,

 β_1 is the slope (a value of $\beta_1 \approx 1$ indicates linearity), and

ε is an error term.

The estimate of slope, $\beta 1$ will be reported along with the corresponding 2-sided 95% CIs. As this is an exploratory analysis, if the 95% CI of β_1 includes 1 and/or the estimate of β_1 is relatively close to 1, PK data may appear to be dose proportional.

The SAS code will be of the form:

The Attainment of Steady-State:

The attainment of steady-state will be assessed by visual inspection of trough concentrations, and statistical assessment. For statistical assessment, linear regression of the individual trough concentrations on Days 3-7 vs time will be conducted, and the slope, 95% CI of the slope, and p-value will be estimated. If the 95% CI of the slope includes 0 and/or the estimate of slope is relatively close to 0, steady-state may appear to be reached.

Exploratory Analyses: Scatterplots

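### The SAP's steady-state and dose-proportionality rules let an imprecise estimate support the favourable statement, mainly in Part B, and the unit of fit for the trough regression is not stated

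*SAP*

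**What the plan says.** SAP 3.1 lists among the pharmacokinetic endpoints "dose-linearity assessment and steady state assessment (after multiple dosing". SAP 6.11 says how each is done.

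- **Steady state.** Troughs are inspected visually, and "linear regression of the individual trough concentrations on Days 3-7 vs time will be conducted". Slope, 95% CI and p-value are estimated. Steady state may then be described as apparently reached on the condition "If the 95% CI of the slope includes 0 and/or the estimate of slope is relatively close to 0".
- **Dose proportionality.** A power model, described as mixed-effects, gives β1 with a two-sided 95% CI. The analysis is labelled exploratory. The data may be called proportional if the CI includes 1 and/or the estimate "is relatively close to 1, PK data may appear to be dose proportional".

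For the trough regression the SAP names no subject term and does not say whether subjects are pooled. For the Day 7 versus Day 1 comparison, the same section says: "The ANOVA model will include factors for subject, day, and cohort". On numbers, SAP 5 says: "Within each cohort, 6 subjects will receive active drug and 2 subjects will receive placebo".

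**The concern.** Both rules treat failure to detect a departure from the null as evidence that there is none. A wide interval is more likely to contain 0 or 1, so fewer subjects, more variability or an inefficient model all help the favourable statement. The and/or wording also lets an interval that excludes the null pass, if someone judges the estimate close enough.

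The unstated unit of fit adds to this for the troughs. Two programmers could follow the text and report different intervals. Pooling without a subject term puts between-subject variance into the residual. Fitting each subject alone leaves 5 points and 3 degrees of freedom, with no rule for combining subjects.

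At stake is the description of two listed endpoints. SAP 6.2.11 also defines Day 7 parameters that presume steady state (average steady-state concentration and steady-state apparent clearance).

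**Working it through.** **Inputs.** Six active subjects per cohort (SAP 5) give 18 in Part B if three cohorts run, and 30 in Part A if five run. Each active subject has predose samples on Days 3-7, so there are 6 × 5 = 30 troughs per cohort. SAP 4 says the sample size has no statistical basis, so there is no power or precision figure to reproduce. All CVs, half-lives and Part B dose ratios below are assumptions. Protocol 3.4 sets the Part A steps after dose 2 at 2, up to 2, and 1.5 times. The step from dose 1 is blacked out and assumed two-fold, giving 2 × 2 × 2 × 1.5 = 12-fold.

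**1. Dose proportionality.** With one value per subject, SE(β1) = σ/√Sxx, where σ = √ln(1 + CV²) and Sxx = 6 Σ(ln dose − mean)².

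Part B at 1:2:4: ln doses are 0, 0.693 and 1.386, so Sxx = 6 × (0.693² + 0 + 0.693²) = 5.77. There are 18 − 2 = 16 df and t = 2.120.

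- CV 30%: σ = 0.294, SE = 0.294/2.401 = 0.122, half-width 0.26.
- CV 60%: σ = 0.555, SE = 0.231, half-width 0.49.

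At true β1 = 1.3, dose-normalised exposure at the top dose is 4^0.3 = 1.52 times that at the bottom dose. The noncentrality is 0.3/SE, which is 2.45 at CV 30% and 1.30 at CV 60%. The noncentral t distribution gives the chance that the CI includes 1:

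| Design | df | CV 30% | 40% | 50% | 60% |
|---|---|---|---|---|---|
| Part B, 1:2:4 | 16 | 0.365 | 0.580 | 0.700 | 0.769 |
| Part A, four cohorts, 1:2:4:8 | 22 | 0.040 | 0.193 | 0.365 | 0.498 |
| Part A, five cohorts, 1:2:4:8:12 | 28 | 0.002 | 0.040 | 0.142 | 0.267 |

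Part B runs from 54-83% at doses 1:2:3 to 5-51% at 1:3:9. With a Part A first step of 1.5 or 3 times, the five-cohort range becomes 0.7-35% or 0.02-16%.

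**2. Troughs.** Under linear one-compartment kinetics, the Day d trough as a share of plateau is 1 − 2^(−24(d−1)/h) for half-life h, for any regimen that repeats every 24 h. The last two columns are the simulated share of trials (40,000 per scenario, raw scale, independent within-subject errors) whose CI includes 0. Between/within CV pairs were 40/20, 50/25, 60/30, 30/30, 40/40, 50/50 and 30/50%.

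| Half-life | Day 3 | Day 7 | Rise | Pooled | With subject intercepts |
|---|---|---|---|---|---|
| 12 h | 93.75% | 99.98% | 1.07× | 97-99.7% | 93-95% |
| 24 h | 75% | 98.4% | 1.31× | 85-96% | 42-87% |
| 36 h | 60.3% | 93.75% | 1.55× | 55-86% | 6-71% |
| 48 h | 50% | 87.5% | 1.75× | 29-75% | 0.8-57% |

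If each subject is fitted alone, 71-91% of single-subject CIs include 0 at 48 h.

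**3. Effect of pooling.** With independent within-subject errors, the pooled residual has 28 df: 5 between subjects with expectation σw² + 5σb², and 23 within with expectation σw². Its expectation is therefore σw² + (25/28)σb², and the SE is inflated by about √(1 + (25/28)σb²/σw²). On the log scale:

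- CVs 40/20: σb² = 0.148, σw² = 0.0392, factor √(1 + 0.893 × 3.78) = 2.09.
- Equal CVs: √1.893 = 1.38.
- CVs 30/50: √(1 + 0.893 × 0.386) = 1.16.

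The simulated mean SE divided by the true SE is slightly lower: 1.98-2.03 (2:1 pairs), 1.35-1.36 and 1.14. On the raw scale it is 1.72-1.90, 1.21-1.29 and 1.08.

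**4. Serial correlation.** With an assumed AR(1) of 0.5 between a subject's consecutive troughs (raw scale, true steady state), the pooled ratio is 1.63 at 50/25, 1.13 at 40/40 and 0.96-0.97 at 30/50, where coverage is 94.8%. A plain subject-intercept fit covers 0 in about 86-87% of trials (90-91% at AR(1) 0.3). A one-sample t interval on the six per-subject slopes covers 95-96%.

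**The case against.** The strongest reply is that little turns on these rules. The conclusions are hedged, troughs are also inspected by eye, proportionality is labelled exploratory, and the estimates and intervals are produced either way. Accumulation is measured directly by Rac and the Day 7 to Day 1 ratio. Neither rule appears among the escalation factors in Protocol 3.4 or in the interim package in SAP 7. All of this stands, and it sets the priority. It does not make inclusion of the null into evidence.

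Four stronger readings are tempting, and the documents do not support them.

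- **The regression wrongly omits a subject effect, so its interval is always too wide.** The wording could mean one fit per subject, which needs no such term. Even a pooled interval is not always too wide (step 4).
- **Steady state is likely to be declared wrongly.** That needs half-lives of about 36-48 h. The documents give no human half-life, and the only accumulation statement (Protocol 1.1.1, rats and dogs, partly redacted) points to little accumulation. At 24 h, Day 7 is already at 98.4% of plateau, so a favourable statement is reasonable.
- **Adding a subject effect repairs the rule.** At 24 h that fit excludes 0 in 13-58% of trials, because the slope measures flatness over Days 3-7 and troughs rise 31% in that window.
- **The handling of values below quantitation is contradictory.** SAP 6.2.10 covers summaries and SAP 6.2.11 covers the pharmacokinetic analysis. The second fits the trough regression more naturally, so at most a detail is missing.

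It is also fair to say that required margins would be partly a matter of preference with six subjects per cohort, since tight ones would often return inconclusive. The fix therefore leaves a margin optional.

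**Conclusion.** The point holds in a limited form, at low priority. Both rules let imprecision, or an undefined judgement of closeness, support the favourable statement. The effect is material for Part B proportionality: the CI includes 1 in 37-77% of trials at true β1 = 1.3 under assumed 1:2:4 doses and CV 30-60%. It is smaller in Part A if all five cohorts run (0.2-27%). For the troughs it is material only at assumed half-lives of about 36-48 h, and the choice of model hardly matters at 12 h or less.

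The unit of the trough fit is unstated. If pooled without a subject term, the model SE can reach about 1.9 (raw) or 2.0 (log) times the true SE. That excess can vanish when within-subject variance dominates and troughs are serially correlated. The direction of the argument about the rules does not depend on the assumptions; the percentages do.

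**What to change.** In SAP 6.11:

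- Delete both rules. Report the trough slope by cohort, and β1, each with its 95% CI. Say that inclusion of 0 or 1 is not evidence of steady state or proportionality.
- Estimate the trough slope within subjects, for example as the mean of the six per-subject slopes with a t interval on 5 df. A subject-effect model that allows for serial correlation would also do. A plain subject-intercept fit can under-cover.
- Describe the slope as flatness over Days 3-7, not as attainment of steady state by Day 7.
- If the sponsor wants a verdict, it should set and justify its own margin in advance, require the CI to lie inside it, and otherwise report inconclusive.

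The cost is a few sentences and lines of code on data already planned. Some results will read inconclusive. The 5-df interval is also wider than the subject-intercept one: with independent errors the two have the same true SE, so the width ratio is about 2.571/2.069 = 1.24.

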6.12. Safety Analyses

The safety analyses will be presented by the treatment received for the Safety Population.

6.12.1. Adverse Events

A treatment emergent adverse event (TEAE) is defined as:

- Any AE that has an onset on or after the first dose of study drug and before EoS/ET visit.
- Any pre-existing condition that has worsened in severity on or after the first dose of study drug and before the EoS/ET visit.

A treatment-related AE is defined as an AE as being related or possibly related to the study drug. If an AE has missing relationship it is assumed to be related to the study drug for analysis purposes.

The following tables will be presented for AEs:

- Overall incidence of TEAEs, severe TEAEs, treatment-related TEAEs, SAEs, and TEAEs leading to early termination.
- Incidence of TEAEs by system organ class and preferred term
- Incidence of treatment-related TEAE by system organ class and preferred term,
- Incidence of Serious TEAEs by system organ class and preferred term
- Incidence of TEAEs by maximum severity and system organ class and preferred term
- Incidence of treatment-related TEAEs by maximum severity and system organ class and preferred term
- Incidence of TEAEs by relationship to study drug and system organ class and preferred term
- Incidence of TEAEs by system organ class and preferred term, combining all placebo subjects in a single treatment group and all drug-treated subjects in a single treatment group, for SAD, MAD, and both SAD and MAD combined
- Listing of TEAEs leading to early termination
- Listing of Serious TEAEs (presented in the Table section of the appendices)

• Listing of Deaths (presented in the Table section of the appendices)

System organ class will be presented in descending order of overall frequency and then alphabetically. Preferred term will be displayed in descending order of overall frequency and then alphabetically within system organ class.

In counting the number of AEs reported, a continuous event (i.e. reported more than once and which did not cease), will be counted only once; non-continuous AE reported several times by the same subject will be counted as multiple events.

If more than one AE is coded to the same preferred term for the same subject, the subject will be counted only once for that preferred term using the most severe and/or most related occurrence for tabulations by severity and by relationship to the study drug.

All AEs will be listed.

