### 5.9 End-of-Study/Early Termination Procedures

End-of-study procedures will be performed on Day 11 of Part A and on Day 35 of Part B.

The following procedures and assessments will be performed:

- Concomitant medications review
- Vital signs measurements (blood pressure, pulse rate, respiration rate, pulse oximetry, and temperature).
- Physical examination
- ECG

- Chest X-ray (PA and lateral) (required for Part A; at the Investigator's discretion for Part B)
- Spirometry
- Clinical laboratory tests
- Coagulation tests
- Urinalysis
- Pregnancy testing (female subjects)
- Adverse event assessment

When possible, end-of-study procedures will be performed in the event of a subject's early termination from the study.

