#### 6 ADVERSE EVENTS

Subjects will be monitored for any AEs from the beginning of confinement until the end-of-study visit. The Investigator or a medically qualified designee will review each event. The Investigator or a Sub-Investigator will assess its relationship to the study drug. Each sign or symptom will be graded for severity, and the date and time of onset, cessation and resolution will be recorded. Treatment of any adverse reactions will be evaluated and managed by a physician, either at the study site or at a nearby hospital emergency room, as appropriate. All non-serious AEs will be reported on a regular basis or as specified by the Sponsor.

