6.2.5. Duration/Study Day/Time

Study day will be calculated as the number of days from first dose of study drug for both Part A and Part B.

- date of event date of first dose of study drug + 1, for events on or after first dose
- date of event date of first dose of study drug, for events before first dose.

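### Both TEAE criteria stop before the EoS/ET visit, so an AE dated at that visit is collected and listed but left out of the TEAE incidence tables

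*SAP*

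**What the plan says.** SAP section 6.12.1 gives two ways for an AE to be treatment-emergent. The first is "Any AE that has an onset on or after the first dose of study drug and before EoS/ET visit". The second is "Any pre-existing condition that has worsened in severity on or after the first dose of study drug and before the EoS/ET visit". Both use *before* as the upper limit.

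Protocol section 5.9 fixes the visit: "End-of-study procedures will be performed on Day 11 of Part A and on Day 35 of Part B". The same procedures are to be done at early termination when possible, and the list includes "Adverse event assessment" alongside physical examination, ECG, spirometry, laboratory tests and chest X-ray (required in Part A, at the investigator's discretion in Part B). Protocol section 6 gives the monitoring period: "Subjects will be monitored for any AEs from the beginning of confinement until the end-of-study visit".

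SAP section 6.12.1 restricts the incidence tables by system organ class and preferred term to TEAEs, and separately lists every AE. The overall summary is to show "Overall incidence of TEAEs, severe TEAEs, treatment-related TEAEs, SAEs, and TEAEs leading to early termination".

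**The concern.** The visit at which the last AE assessment takes place lies outside the window used to count AEs. An event that starts or worsens at that visit is recorded under the protocol but meets neither TEAE criterion.

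TEAE incidence is the first-named safety endpoint in SAP section 3.1, so the summary tables for that endpoint could leave out an event that the trial collected. Two situations matter most:

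- **Findings first made at the visit.** Under protocol section 6.1.1 an AE can be an unfavourable sign such as an abnormal test result. A finding first detected by an EoS test may well carry that day's date. For chest X-ray, TSH and physical examination the SAP plans listings only (sections 6.12.6 and 6.12.7), so the TEAE tables are the only planned incidence summary in which such a finding would appear.
- **AEs that cause early termination.** If the ET visit falls on the day the AE began, a flag based on dates would remove that AE from the count of TEAEs leading to early termination.

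**Working it through.** The plan gives no figure to reproduce. The check compares the collection window with the counting window, looks for any rule that closes the gap, and then sizes it.

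**1. Does another rule bring the event back?**

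- SAP 6.2.4 pools ET with EoS in tabulations but does not change the TEAE window.
- SAP 6.2.6, on missing dates, decides only whether an AE started after first dosing. It says nothing about the end of the window.
- SAP section 8 declares no change to the protocol analysis. The protocol sets no TEAE window of its own.
- In protocol section 6, *until* the visit does not say whether the visit is included.

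Nothing restores the event. It appears in Listing 16.2.7.1 and not in the TEAE tables.

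**2. Is *before* judged by date or by time?** The SAP does not say. The protocol requires that "the date and time of onset, cessation and resolution will be recorded". In the SAP, "Study day will be calculated as the number of days from first dose of study drug for both Part A and Part B", which uses dates only. Judged by time, only onsets from the start of the visit are lost. Judged by date, the whole visit day is lost:

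- Part A, Days 1 to 11: 1/11 = 9.1% of on-study days.
- Part B, Days 1 to 35: 1/35 = 2.9% of on-study days.

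These are shares of days, not of events.

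**3. How much of the listed-only postdose schedule falls at EoS?** Counted from protocol sections 5.9, 5.10.3 and 5.10.5 and the events schedules (Tables 6, 7, 9 and 11):

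| Assessment | Scheduled postdose | At EoS |
|---|---|---|
| Part A chest X-ray | Day 11 | 1 of 1 |
| Part A physical examination | 24 h, 48 h, Day 11 | 1 of 3 |
| Part B TSH | Day 35 | 1 of 1 |
| Part B physical examination | Days 2, 4, 7, 9, 14, 35 | 1 of 6 |

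The scheduled Part B chest X-ray is on Day 9, inside the window.

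**4. What can one omitted event do to a reported incidence?** The ceiling is 1/n, reached only if the subject has no other event counted in that row. Group sizes follow from 6 active and 2 placebo subjects per cohort, with placebo pooled across cohorts (SAP 6.3). The plan allows up to 5 cohorts in Part A and 3 in Part B.

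| Group, all cohorts run | n | Ceiling (percentage points) |
|---|---|---|
| One dose group | 6 | 1/6 = 16.7 |
| Pooled placebo, Part A | 5 × 2 = 10 | 1/10 = 10.0 |
| Pooled placebo, Part B | 3 × 2 = 6 | 1/6 = 16.7 |
| All active, Part A | 5 × 6 = 30 | 1/30 = 3.3 |
| All active, Part B | 3 × 6 = 18 | 1/18 = 5.6 |
| All active, both parts | 30 + 18 = 48 | 1/48 = 2.1 |
| All placebo, both parts | 10 + 6 = 16 | 1/16 = 6.3 |

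With only four cohorts in Part A, pooled placebo has n = 4 × 2 = 8 and the ceiling is 1/8 = 12.5 points.

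**5. Serious events.** The overall summary names SAEs without the TEAE restriction, so a visit-day SAE could be counted there. It need not be, because Tables 14.3.1.1a and 14.3.1.1b are titled as TEAE summaries. It would not be in the serious-TEAE table by system organ class and preferred term. The title of Listing 14.3.2.1 covers all SAEs, but the text of SAP 6.12.1 describes the listing as limited to serious TEAEs.

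**The case against.** The strongest reply is that this is one word at a boundary, with little behind it.

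- *Until* in the protocol and *before* in the SAP may mark the same limit, and an AE assessment at the last visit serves largely to capture events since the previous contact, which remain TEAEs. That is fair, but the visit's own tests can yield new findings dated that day, and the SAP wording excludes those.
- There is some support for judging by time: the protocol records onset time, and SAP 6.2.6 speaks of a missing AE start date or time. On that reading the 9.1% and 2.9% do not apply, and an AE that leads to termination would ordinarily have started before the ET visit. This reduces the weight. It leaves findings timed at the visit itself, and the SAP still does not state the rule. The AE tables are to be validated by independent programming, and two programmers could build different flags from this text.
- Nothing is lost from the data. All AEs, X-rays, TSH results and examination findings are listed, no AE test is planned, and the dose-escalation review in protocol section 3.3 uses all adverse events and not the TEAE tables. This stands, and it limits the consequence to the summary tables.
- Changing *before* to an inclusive limit does not settle date versus time, gives no end point for a subject who has no ET visit, and does not reach possibly related SAEs reported within one month after the study (protocol section 6.2). These are real limits of the edit, but they do not argue for keeping the present wording.

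**Conclusion.** The point holds and is minor. By its wording, the SAP excludes from the TEAE tables any AE with onset or worsening dated at the EoS/ET visit, although the protocol collects AEs at that visit. The error can only understate TEAE incidence.

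The number of events affected is probably small and cannot be estimated from the documents. The shares of days assume a flag based on dates, and the percentage-point figures are per-event ceilings that assume full enrolment. No hypothesis test and no dose-escalation decision described in the documents depends on the flag.

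**What to change.** In both TEAE criteria of SAP section 6.12.1, replace the *before* limit with *up to and including the EoS/ET visit*, leaving the onset and worsening conditions as they are. Add a sentence saying whether the comparison uses date or time.

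If dates are used, the window becomes Days 1 to 11 in Part A and Days 1 to 35 in Part B, and the programming change is one operator (< to <=). The cost is an edit to two bullets plus the added sentence, with no new data. The only downside is that TEAE counts may be slightly higher.
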